Maternal DHA levels are related to lower change in infant FM: Infant body composition was measured using the Pea Pod (n=62) at birth and 3 months. No prenatal DHA supplementation was provided and maternal RBC DHA was measured at 36 weeks in pregnancy and categorized by the median as high (>50th percentile) or low (<50th percentile). We first explored the main effect of maternal DHA status on differences in the change in infant FM. Offspring born to mothers with a high DHA status had a lower change in FM when compared to offspring born to mothers with a low DHA status. With the known effect of excessive GWG on infant FM, next we explored the interaction of maternal DHA status and GWG category on the change in infant FM. Maternal GWG was categorized as appropriate or excessive based on the 2009 IOM guidelines. Using ANCOVA, we examined the main effects and interaction of maternal RBC DHA status and GWG category on the change in infant FM. Confounding variables included in the model were maternal pre-pregnancy BMI, GWG, 3rd trimester maternal measured DHA, father's BMI, maternal race, household income, gestational age at birth, infant gender, infant age at test, and baseline variable of interest (ie., infant FM). The interaction was significant (p=0.028). In post-hoc analysis, no difference was found by maternal DHA status in offspring exposed to appropriate GWG. However, in offspring exposed to excessive GWG, infants exposed to low maternal DHA status had a greater increase in offspring FM (Δ 1499.0 g) when compared to infants exposed to high maternal DHA status (Δ 1026.4 g; p=0.038). A similar effect was found for body mass, however, no difference for the change in FFM was found. Therefore, in the offspring exposed to excessive GWG and high DHA status, the lower change in body mass was due to a lower accrual in FM and not FFM. See Table 2 for a summary of these results. These data are preliminary but promising considering no maternal prenatal DHA supplementation was provided.

and DHA status.					
Infant		Weight gai	in status	D L	
variable	DHA status	Appropriate($n=25$)Excessive ($n=37$)		r value	
Change in	<50 th percentile	2943.1 ± 810.9	3589.1 ± 965.3	p-int=0.045; p=0.060 post-hoc	
body mass (g)	>50 th percentile	3146.7 ± 926.9	2961.7 ± 796.6	by DHA status	
Change in %fat	<50 th percentile	12.9 ± 6.2	15.5 ± 7.0	p-int=0.033; p=0.083 post-hoc	
	>50 th percentile	15.2 ± 7.2	11.1 ± 6.1	by DHA status	
Change in FM (g)	<50 th percentile	1189.5 ± 549.9	1499.0 ± 622.4	p-int=0.028; p=0.038 post-hoc	
	>50 th percentile	1330.4 ± 640.7	1026.4 ± 539.3	by DHA status	
Change in FFM (g)	<50 th percentile	1432.0 ± 435.3	2049.8 ± 497.0		
	>50 th percentile	1167.0 ± 519.2	2034.8 ± 430.3	p-int=0.292	
Values are presented at means + standard deviations					

Table 2. Change in infant body composition from birth to 3 months of age based on maternal GWG

P-int=P value for the interaction between DHA status and Weight Gain Category (appropriate vs. excessive) Confounding variables included in the model: maternal pre-pregnancy BMI, GWG, 3rd trimester maternal measured DHA, father's BMI, maternal race, household income, gestational age at birth, infant gender, infant age at test, and baseline variable (ie., Body mass).

Maternal DHA levels and changes in central FM: Further analysis of [name] unsupplemented pregnancy cohort are reported here. Skinfolds were measured on the central and peripheral part of the infant's body to assess AT distribution using standardized procedures. Using ANCOVA, we examined the main effects of maternal RBC status and infant gender on the change in central FM. The same confounding variables were included from the prior analysis. The p values for the main effects of DHA status and gender were p=0.282 and p=0.076, respectively. We next explored the interaction of maternal DHA status and gender on the change in central FM. This interaction approached significance (p=0.085). In post-hoc analysis, no difference was found by maternal DHA status in males but a clear difference was found in females. Females born to mothers with high DHA status had a lower change in central FM (Δ 3.6 mm) compared to females born to mothers with a low DHA status (Δ 5.7 mm; p=0.053). The main effect of gender detected in the first model appears to be driven by the difference found in females. No difference for the change in peripheral FM was found. See **Table 3** for a summary.

Table 3. Change in central FM from birth to 3 months of age.						
DHA status	Change in ce	P value				
<50 th percentile	4.5	P=0.282				
>50 th percentile	3.6					
	Male (n=36)	Female (n=22)	$p_{int=0}^{int=0}$ or $p_{int=0}^{int=0}$ or $p_{int=0}^{int=0}$			
<50 th percentile	3.7 ± 2.3	5. 7 ± 2.2	hoc for difference in			
>50 th percentile	3.6 ± 2.2	3.6 ± 2.0	females by DHA status			
Values are presented at means ± standard deviations P-int=P value for the interaction between DHA status and Gender (male vs. female)						

Confounding variables included in the model: maternal pre-pregnancy BMI, GWG, 3rd trimester maternal measured DHA, father's BMI, maternal race, household income, gestational age at birth, infant gender, infant age at test, and baseline distribution variable (ie., Central FM).

What these data suggest: There are identified risk factors that are related to greater offspring FM; two of these risk factors are catch-up growth^{117,118} and exposure to maternal excessive GWG^{9,14}. Our preliminary data suggest a protective effect of DHA exposure for programming a favorable offspring body composition phenotype with excessive GWG during early growth. Infants born preterm and likely to experience high rates of weight gain were protected against excessive FM accumulation. In another cohort, infants exposed to excessive GWG had lower FM accumulation detected early, at 3 months old, when mothers had a high vs. low DHA status and were exposed to excessive GWG. At 3 months old we detect a 672 g difference in body weight that is largely accounted for by the change in FM of 472 g. Therefore, at 3 months old, there is already a more than 1-pound difference in FM between these groups and DHA appears to be mediating this difference.

It is known that FM location in adults⁴ and children^{5,6} is an important predictor of disease risk and development. Although the main effect of maternal DHA status on the change in central FM was not significant, it is important to note that women in our pilot study were a sample of convenience who were not being supplemented with DHA. No one has examined AT distribution in a cohort supplemented with high levels of DHA. Further, exploration of gender shows in female offspring born to mothers with a high DHA status, they had a lower change in central FM when compared to female offspring born to mothers with a low DHA status. No effect was found in males. Our preliminary data provide interesting differences detected early in infancy that warrant follow up in a larger sample exposed to high vs. low prenatal DHA supplementation.

D3) **Recruitment for the current proposal**: Our study will enroll subjects from the RCT; "*Docosahexaenoic acid (DHA) supplementation in pregnancy to reduce early preterm birth*" (NIH R01 HD83292-01; n=1200 at 3 study sites). The current ancillary grant proposes to follow offspring from the Kansas City site where the expected enrollment will reach ~n=600. The parent study partnered with Juntos to recruit Hispanic pregnant women and they have been highly successful in recruiting a large number of Hispanic pregnant women, whom only speak Spanish. The GAINS study must be able to recruit the offspring born to this population. Enrollment may occur at any of the 4 time points: 2 weeks, 6 months, 12 months, or 24 months. If parents decide not to participate when contacted by study personnel, but agree to be contacted when the infant is older, the study personnel will contact them at 24 months.

The parent study (ADORE) is a Phase III Double Blinded Randomized Controlled Clinical Trial where women will be randomized to either a low or high dose DHA (1,000 mg/d or 200 mg/d). The primary outcome of this RCT is to move early pre-term birth to late pre-term birth. No targeted recruitment of women at risk for pre-term birth will be done (see **Table 1** for inclusion/exclusion criteria). Anyone meeting the inclusion criteria will be enrolled. At enrollment of the parent RCT, all participants will be asked if they can be contacted for other related studies. Their decision is recorded in the consent and a database. Late in pregnancy, women enrolled in the RCT will be approached. Based on [name] prior KUDOS RCT pregnancy supplementation study, the number enrolled was 350 with 86% of the sample retained at birth for follow up in the postnatal period. The study team has full confidence the recruitment goal can be met (see c7a "Power calculations" and D9 "Study Challenges" for further discussion).

Recruitment process: Both parents must give their permission unless one parent is deceased, unknown, incompetent, or not reasonably available, or when only one parent has legal responsibility for the care and custody of the child. If only one parent is signing, the reason will be well documented in the subject's chart/source documentation. Both signatures will be

obtained prior to any research procedures taking place on the child. One or both parent signatures may be obtained via REDcap as long as:

a. A member of the study team calls the parent(s) and walks through the entire document over the phone, answering questions and making notes about the parent's (or parents') questions. (This will be well documented in the subject's chart/source documentation);b. Time and date of the conversation are recorded; AND

c. The study team member obtaining consent writes a note on the consent form stating that the parent's (or parents') consent was obtained by phone/REDcap on the date the parent(s) signed.

At least one copy of the signed consent form (with both signatures) will be provided to one of the parents. If signatures are obtained via REDcap, then this signed consent form can be provided via mail or secured email.

Table 4. Current parent trial enrollment at Kansas City site						
Month/year of visit	Expected ADORE enrollment	Actual # enrolled English	Actual # enrolled Spanish			
Yr1: June 2016 - May 2017	108	70	28			
June-17	9	8	4			
July-17	9	3	14			
August-17	9	4	8			
September-17	9	11	10			
October-17	9	5	10			
November-17	9	6	10			
December-17	9	2	7			
January-18	9	9	3			
February-18	9	5	5			
March-18	9	9	7			
April-18	9	7	6			
May-18	9	11	6			
June-18	9	14	7			
July-18	9	6	3			
Total Enrollment	234	170	128			

Current recruitment from the parent RCT: At the time of this revised proposal, the trial has enrolled 298 pregnant women at the Kansas City site and 299 pregnant women at the other two sites combined. The Kansas City site is on track to recruit about 50% of the trial participants instead of the expected 33%. Of the 298 pregnant women at the Kansas City site, 43% (n=128) are Spanish speaking. We originally proposed to recruit n=180, accounting for a 33% attrition rate in the power analysis. The success of the parent RCT in recruiting Spanish speaking pregnant women allows us to answer our primary aim in a second group of women, but we must be able to recruit the offspring born to this

population. Therefore, we are increasing our sample size by n=180 for a total sample of n=360. See **Table 4** for a summary of recruitment at the Kansas City site.

D4) **Standardized training and quality assurance**: [name] has considerable experience (over 10 years) assessing body composition in different populations using different systems. Dr.

[name] will provide initial and ongoing training for all Research Assistants regarding assessment of body composition. All Research Assistant's will undergo standardized body composition training and annually, re-fresher training will be completed. For quality control purposes, daily scans will be performed on the DXA system using the Quality Assurance block provided by the manufacturer to simulate fat and fat-free soft tissues, respectively^{119,120}. Movement is not tolerated by the DXA system however total body scans in newborns and toddlers are relatively short (~3 minutes). Co-I [name] has considerable experience (n=1,540 scans from birth to 6 years old) obtaining DXA images in infants, toddlers, and children. She will be in charge of assisting [name] to develop protocols to ensure a valid DXA scan is captured at each age time point.

D5) **Assessments**: Infant body composition and AT distribution will be measured at 2 weeks and 6, 12, and 24 months using dual energy x-ray absorptiometry (DXA). Collection and analysis of maternal RBC will be completed as part of the parent RCT. Maternal blood will be collected at delivery and analysis will be completed after delivery. Upon completion of this protocol, [name] will have access to study assignment (1,000 mg/d or 200 mg/d). An overview of study visits is listed in **Table 5**.

Table 5. An outline of study visits and procedures.					
Study procedure	2 wks	6 months	12 months	24 months	
Enrollment & Consent	Prior to any study visit				
DXA scan	•	•	•	•	
PeaPod	•	•			
Anthropometry & skinfolds	•	•	•	•	
Diet recall & questionnaires	•	•	•	•	
Incentives	\$125	\$125	\$125	\$125	

D5a) Dual energy x-ray absorptiometry to measure total body fat and AT distribution: Dual energy x-ray absorptiometry (DXA; Prodigy, Madison, WI, encore software version 13.60) will be used to measure body composition and regional AT distribution. The DXA is located within the Dietetics & Nutrition Clinic inside the Smith West building at KUMC. Using specific anatomic landmarks as previously described, regions including the arms, legs and trunk will be demarcated⁸. Calculations for FM in each region and summed for regions comprising the central (trunk) and peripheral (arms plus legs) will be completed. If a child moves during the scan the scan may need to be re-done but no more than 8 total scans will be given over the duration of the study.

D5b) GWG: GWG will be calculated by subtracting the self-reported pre-pregnancy body weight from the last weighed measurement in the clinic (pulled from the EMR) prior to delivery. GWG will be classified according to 2009 IOM GWG guidelines as appropriate or excessive¹²¹.

D5c) Anthropometry: Body weight will be assessed on the same calibrated scale throughout the study duration (Detetco Scales, Webb City, MO). Length will be measured using an infant length board (Shorr Productions) and at 24 months old, standing height will be measured using a wall mounted stadiometer (Accu-Hite, Seca Corp, Hanover, MD). Subjects will remove shoes and be centered on the stadiometer. Height will be recorded to the nearest 0.1 cm. Two measurements will be taken and the average will be recorded.

D5d) Skinfolds: Six skinfolds will be measured to represent AT distribution in order to compare to larger trials that do not have DXA. [name] has published using these methods to assess infant FM distribution³ and it has been argued skinfolds are a valid metric of regional FM⁷⁴. All measurements will be collected using standardized procedures to our Laboratory and will take place on the same day as the body composition assessment by DXA using standardized procedures. All skinfolds will be identified using anatomical landmarks and taken on the right side of the body using Lange calipers (Beta Technology, Santa Cruz, CA). Skinfolds will be taken in order from head to toe and then repeated in that same order. If two skinfold measurements differ by more than 1 mm, a third measurement will be taken. The two measurements within 1 mm will be averaged and used for analysis. Biceps and triceps skinfolds will be measured at the midline of the anterior and posterior surface of the arm, respectively, on the mid-point between acromial process of the scapula and olecranon process of the ulna. Subscapular skinfold will be measured at the lower angle of the scapula. Suprailiac skinfold will be measured anteriorly to the midaxillary line and superiorly to the iliac crest, along the natural cleavage of the skin. The thigh skinfold will be measured at the mid-point between patella (knee cap) and inguinal crease at the anterior surface of the thigh. Flank skinfold will be measured immediately above the iliac crest at the mid-axillary line. Central FM will be calculated by adding the subscapular, suprailiac and flank skinfolds and dividing by two. Peripheral FM will be calculated by adding the thigh, biceps and triceps skinfolds and dividing by three.

D5e) 24 hour dietary recall: One multiple-pass 24-hour dietary recalls will be collected by trained research staff at each visit to characterize energy and nutrient intake. 24-hour recalls accurately estimate dietary intake^{122,123} and contain less reporting bias than diet records ^{122,124}. The recalls will be entered into the Nutrition Data System for Research (NDS-R, version 2018, Minneapolis, MN) for macro- and micronutrient analysis. At 6 and 12 months, a feeding questionnaire will be given to assess infant feeding practices (breastfeeding, formula, etc) and introduction of solids. [name] has successfully used this method to assess children's diet in her prior RCT from birth to 5 years old.

D5f) Fatty acid analysis: Maternal blood taken at enrollment and birth, and cord blood will be analyzed a part of the parent NIH study. RBCs will be separated from plasma and buffy coat by centrifugation (3,000×*g*, 10 minutes; 4°C), frozen, and stored under nitrogen at -80°C until analysis. Phospholipids from erythrocytes will be isolated according to a modified Folch method^{4z}, and fractionated by thin-layer chromatography, transmethylated with boron trifluoride-methanol, and the resulting fatty acid methyl esters (FAME) separated and quantified using a Varian 3900 gas chromatograph with an SP-2560 capillary column (100 m, Sigma Aldrich) and a Star 6.41 Chromatography Workstation for peak integration and analysis^{4z}. Individual peaks will be identified by comparison with qualitative standards (PUFA 1 and PUFA 2, Sigma Aldrich) and a weighed standard mixture (Supelco 37 Component FAME mix, Sigma Aldrich) will be used to adjust fatty acids for area/weight to calculate a final weight percent of total fatty acids. *The cost of DHA analysis is covered by the parent NIH study*.

D5g) Questionnaires: Questionnaires will be given at the baseline visit to assess maternal and familial characteristics. Examples of information collected include family history of disease, stress during pregnancy, other children in the home, and biological father's height and weight. Maternal health history information collected as part of the parent RCT will be reviewed.

D5h) Illness Assessment: In order to control for the potential impact of child's illness on growth, we will collect illness data. Medical records will be requested upon completion of study for each subject enrolled in the follow-up trial; medical records for any participants lost to follow-up will

be requested upon Release of Information form expiration. Medical records are reviewed for adverse events upon receipt and all adverse events are recorded by body system and coded by diagnosis within body system. For each adverse event, the following information is recorded: diagnosis, body system code for the diagnosis, whether the event was a serious adverse event, event start date, event ongoing dates if applicable, event stop date, treatment including names of medications, age of child in mos at the start of the event, and location of service for the event (ex. Hospital, pediatric clinic, urgent care clinic). Records are coded by one individual and then checked for accuracy by a second person.

D5i) Air Displacement Plethysmography to measure total fat mass and fat-free mass: Pea Pod (COSMED) will be used as an additional method to measure body composition at 2 weeks and 6 months. The Pea Pod assesses body volume and density to calculate fat mass and fat-free mass. The test will be conducted according to manufacturer guidelines.

D5j) Steps to maximize retention: At KUMC, we use the ClinCard system, which works like a debit/credit card. At study enrollment, subjects are given a card that looks like a debit/credit card with a number unique to each participant. At the completion of study visits with incentives, staff log in and the card is loaded with the respective stipend amount within 24-48 hours. The card can be used anywhere Visa/Mastercard is accepted. For each study visit completed, subjects will be paid \$125 (total \$500 if all visits are completed). If a DXA scan is unable to be acquired during any study visit, subjects may be asked to return at a later date and will receive an additional \$50 for returning. Please refer to **Table 5** for the incentive schedule.

The *scientific rigor* of this application is high. We are following a cohort born to women participating in an already NIH funded and approved RCT that has been vetted for safety and efficacy which provides strength to this proposal. For the outcomes of this proposal, we are using DXA to assess body composition and distribution which is the only precise technique for evaluating amount and location of body fat.

Table 6. Research timeline and activities.							
Research Activities	2017	2018	2019	2020	2021	2022	2023
icocaren netivities							
Hiring/train personnel	—						
Develop data collection	_						
protocols							
IRB submission	—						
Recruitment/screening							
Data collection							
Data collection							
Data entry							
Data collection ends							
Data analysis and							
writing							
Manuscript prep &							
submission							

D6) **Study timeline**: Listed in **Table 6** is the timeline for the study.

D7): **Statistical analyses**: The primary purpose of this study is to determine if there are differences in the offspring FM at 24 months when exposed prenatally to high vs. low DHA supplementation and if maternal GWG status impacts this relationship (appropriate or excessive GWG).

D7a) **Aim 1 analysis:** Using a two-way analysis of variance (ANOVA) on the 24 months FM, we will test for a statistical interaction between GWG group and DHA dose. The specific interaction from this ANOVA will test the contrast to **investigate if the supplement of 1000 mg DHA/day compared to 200 mg DHA/day during pregnancy can reduce infant FM at 24 months and specifically if this reduction is greater in offspring exposed to excessive GWG versus appropriate GWG.** A two sided t-test statistic (alpha=0.05) is calculated from the appropriate contrast from the two-way ANOVA (GWG and DHA).

D7b) **Aim 2 analysis:** A three-way analysis of variance (ANOVA) on the 2 year central FM, we will test for a statistical interaction between both GWG and DHA dose and offspring gender and DHA dose.

D7c) **Longitudinal analysis:** Additionally, we will perform a linear mixed model to explore differences between the high vs. low supplement groups for infant FM and distribution. The dependent variable will be infant FM or infant central FM and the independent variable will be DHA group (fixed effect) and time (4 visits: 2 wks, and 6, 12, and 24 months). The model will include the fixed effects of treatment, time and the treatment-time interaction, with the subject effect treated as random to account for the dependence among repeated observations. This analysis allows for unbalanced data (allows for missing data). We will use exploratory analyses to investigate, in a univariate fashion, covariates. GWG and infant gender will be included as well as other potential covariates including parity, maternal age, pre-pregnancy BMI, parity, education level, maternal diet, infant diet, infant age at test, gestational age at birth, and socioeconomic status. An auto-regressive covariance structure will account for unevenly spaced visits. For missing outcome data, the data vector will be used to impute the missing value. Infant gender will be explored both as a confounder and as an effect modifier to account for differences in growth rates. We will analyze the data without confounding variables and repeat the analysis with confounding variables.

D7d) **Power calculation:** We performed a power analysis based on pilot data reported in **Table 2**. We calculated a total of n=120 would be required to answer the primary aim. Of the total n=120, we anticipate n=54 will experience appropriate GWG (45%) and n=66 will experience excessive GWG (55%) with each approximately equally allocated to low and high DHA supplementation groups. For the given effect size (population mean differences of -168 vs 304 grams), the power is 0.815. This means that 81.5% of studies would be expected to yield a significant effect to detect an interaction, rejecting the null hypothesis that the two population means are equal. The test is two-sided. Allowing for 33% attrition, this increases the sample size to n=180. To answer the primary aim in a second group of Spanish speaking subjects, we will increase the sample size by n=180 for a total sample of n=360.

D8) **Study challenges**: We do not anticipate any major limitations as we developed strategies to successfully minimize issues that arose in the KUDOS follow-up, and applied these to the ADORE trial. The current proposal will follow the successful recruitment, retention, and data collection framework developed in the KUDOS trial and perfected in the ADORE trial. Recruitment of our study is reliant upon the successful recruitment of the parent RCT study. Co-I [name] is the PI on the parent study we will be recruiting from. [name] has successfully completed multiple RCT in pregnant women with high rates of monthly recruitment and retention rates. The average monthly recruitment for her KUDOS trial was 8-12 women/month, with n=350 recruited and n=301 were retained (86% retention rate). The study team has full confidence the recruiting goal of this project can be met. We anticipate some telephones being disconnected, but we obtain additional telephone numbers from subjects for relatives and friends. We expect that there will be attrition from the sample over time; however, our experienced team works to minimize this by adhering to principles that maximize retention of participants in longitudinal studies. These principles include the establishment of an identity for the study (there is a logo and an acronym that participants can readily recognize), maintenance of consistent contact with participants by the same team members, and provision of sufficient payments to participants in compensation for time, travel, and effort (participants will be paid \$125 per visit). In all past RCTs with longitudinal follow-ups, we have been able to retain between 80% to 88% of the participants consented into the follow-up into the second year.

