C1c) Capsule records and accountability: The Investigational Pharmacy at The University of Cincinnati sends capsules to each enrolled subject on a regular schedule until they give birth; and the bottles and any remaining capsules are returned by mail to the Investigational Pharmacy in a self-addressed envelope provided with the capsule mailing, the remaining capsules counted, the number of capsules remaining recorded and the capsules destroyed. Records of capsules mailed to and received back from subjects are entered into the study database with a flag to investigators at the subject's study site. Investigators at each site review the database and contact subjects who do not return their capsule bottle. Study personnel contact the subject by telephone early within the first month and monthly thereafter to determine if there are any problems and encourage compliance. The study investigator, study site staff and subjects do not know which capsules are being consumed by each patient. The Investigational Pharmacy at the University of Cincinnati receives all bottles of capsules directly from DSM, Columbia, MD and maintains packing receipts for study products.

C1d) Randomization for ADORE: Pregnant women are randomized to one of two arms (groups) with a maximum number of pregnant women n_{max} =1200 (we plan for 1355 enrollments due to expected dropout). Each study site location has a separate randomization code. Using a Bayesian Adaptive Design, at each interim analysis a decision is made. Depending upon the birth outcome the randomization structure is updated. The primary endpoint, percentage of ePTB, is used to drive the adaptive randomization. After we have 150 women in each group enrolled the data will be analyzed and an updated randomization schedule will be used. The arm that looks to be the best will get more pregnant women allocated to it in this subsequent randomization. A new adaptive randomization schedule is updated every 13 weeks, using up to date outcome data, until the trial is stopped.

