C1e) Implementation: An initial allocation table would be generated (Master allocation table) with all the factors being considered (i.e. maximum sample size, endpoint etc), this allocation table would be attached to our eResearch tool. Once every patient gets an enrolled status they would be assigned to an ARM (Arm A, Arm B) using the randomization module within eResearch. After enrolling 150 patients, the latest data from the system would be analyzed to generate a new allocation table; this new table would be appended (ignoring all the unused assignments on the allocation table) to the existing allocation table that is already being used, this process would be repeated at every 13 weeks, until we reach the end of the trial.

C1f) Attrition: If a patient withdraws from the study prematurely, the assessments described at delivery that apply will be obtained if available and the subject has not requested her data not be obtained. This, and the requirement to obtain medical records for adverse events during pregnancy and following birth of the infant, will be explicit in the consent form subject to any provisos made by the Central IRB and HIPAA. If the subject is withdrawn due to an adverse event(s), the patient will be monitored until the adverse event has resolved or until the event is determined to be due to a stable or chronic condition. The reason for patient discontinuation will be documented. If a patient withdraws from the study, the patient's study number will not be reassigned.

D) Approach/Preliminary studies to support the proposed study

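### Allocation in the parent trial can change every 13 weeks, yet D7c and any overall or within-excessive-GWG high-versus-low DHA contrast have no randomisation-period term

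*Combined protocol and SAP*

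**What the plan says.** Section C1d describes a Bayesian adaptive design driven by early preterm birth. After a first analysis, "The arm that looks to be the best will get more pregnant women allocated to it in this subsequent randomization", and "A new adaptive randomization schedule is updated every 13 weeks" until the parent trial stops. No floor or cap on the ratio is given. C1e describes the mechanics: "this new table would be appended (ignoring all the unused assignments on the allocation table) to the existing allocation table".

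The two sections place the first update differently. C1d has "After we have 150 women in each group enrolled the data will be analyzed"; C1e has "After enrolling 150 patients, the latest data from the system would be analyzed to generate a new allocation table". Section D3 reports 298 women at Kansas City and 299 at the other two sites, 597 in all, which is past either trigger.

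For the analysis, D7 gives the primary purpose as to "determine if there are differences in the offspring FM at 24 months when exposed prenatally to high vs. low DHA supplementation" and to ask whether GWG status alters this.
- D7a is a two-way ANOVA (GWG, DHA). The one statistic it specifies is the interaction contrast.
- D7b is a three-way ANOVA on central fat mass and tests GWG × DHA and gender × DHA.
- D7c is a mixed model with DHA group, time and their interaction. Time there means the four visits. The covariate list is open but names neither enrolment date nor allocation schedule.
- D7d reports power 0.815 and takes the two DHA arms as about equal within each GWG group.

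**The concern.** When the ratio changes over calendar time, the arm favoured later holds a larger share of late enrolees. If late enrolees' children differ in fat mass for any reason unrelated to DHA, a pooled comparison of arms picks up part of that difference. It does not matter that the adaptation follows preterm birth and not fat mass; it is enough that both allocation and outcome move with time.

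The exposed comparisons are the overall high-versus-low difference named in D7's purpose statement, the treatment effect in D7c, and the comparison within excessive GWG on which the central hypothesis in the Specific Aims rests. In D7c, drift that is the same at every visit cancels from the treatment-by-time interaction but not from the treatment effect. The bias can go either way, depending on which arm was favoured and on the direction of drift.

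**Working it through.** **The plan's own figure.** D7d's 0.815 can be reproduced as a two-sample t-test of 54 against 66 with a 472 g difference (304 + 168) and an SD of √(622.4² + 640.7²) = 893.2 g, which gives 0.815. That SD is inferred; D7d states none. A four-cell contrast with 27/27/33/33 infants and SD 590 g gives 0.58. Because the SD behind 0.815 is unknown, the cost of unequal arms is given below as a change in standard error (SE), not in power.

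**Case mix (Table 4).** The documents say: "Of the 298 pregnant women at the Kansas City site, 43% (n=128) are Spanish speaking". By period the Spanish-speaking share is:
- year 1: 28/98 = 29%;
- June–December 2017: 63/102 = 62%;
- January–July 2018: 37/98 = 38%.

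That is a rise and a fall, and it describes language, not fat mass.

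**Illustration (assumed inputs).** 98 women at 1:1 (year 1), then 200 at share p to one arm; a lasting 0.3 SD step in fat mass at the change; SD 590 g (root mean square of the four fat-mass SDs in Table 2; no 24-month SD is given), so the step is 177 g; 240 analysed, about 360 less 33%; 55% excessive GWG.

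Bias = 177 g × (late share in favoured arm − late share in other arm). At p = 60%: 120/169 − 80/129 = 71.0% − 62.0%, giving 15.9 g. SE = 590 × √(1/n₁ + 1/n₂); with 56.7% of 240 in one arm (136.1 and 103.9) this is 76.9 g. Type I error is from the noncentral t at bias/SE.

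| p | Late shares | Bias | SE, overall | Bias/SE | Type I error |
|---|---|---|---|---|---|
| 60% | 71.0 vs 62.0% | 15.9 g | 76.9 g | 0.21 | 0.055 |
| 67% (2:1) | 73.1 vs 57.6% | 27.4 g | 78.1 g | 0.35 | 0.064 |
| 75% | 75.4 vs 50.5% | 44.0 g | 80.9 g | 0.54 | 0.084 |

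- **Within excessive GWG:** same grams, larger SE; bias/SE 0.15/0.26/0.40, type I error 0.053/0.058/0.069.
- **Aim 1 interaction:** bias 0 if drift is common to both GWG groups. If drift occurs in one group only, bias/SE is 15.9/154.5, 27.4/157.1 and 44.0/162.5 = 0.10/0.17/0.27, type I error 0.051/0.053/0.058.
- **Change placed at September 2017 (160 then 138 women):** overall type I error 0.056–0.091; interaction at most 0.060.
- **0.1 SD step:** overall bias 5/9/15 g, type I error at most 0.054.
- **1:1 throughout:** bias 0.

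**Language mix as the only source.** The share goes from 28.6% to 100/200 = 50.0%, a change of 21.4 points. With an assumed 200 g difference between language groups: 0.214 × 200 g × the share differences = 4/7/11 g. With the September 2017 split it is 1/2/3 g. A 177 g step from language alone would need 177/0.214, about 826 g, between groups.

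**Precision with unequal arms.** SE inflation = 1/(2√(p(1−p))): +2.1% at 60:40, +6.1% at 2:1.

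**Cost of period and period × GWG in D7a.** Simulated at n=120 with 1:1 for the first quarter and then 67%, SD 590 g, and the Table 2 interaction of (1499.0 − 1026.4) − (1189.5 − 1330.4) = 613.5 g. The interaction SE rises by about 3% with 3 blocks, 8% with 8 and 15% with 14. Power falls from about 0.76 to about 0.74, 0.70 and 0.64.

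**The case against.** The strongest reply is that the tests the plan actually specifies are hardly exposed. D7a's one stated statistic and both D7b targets are interactions, and D7c is described as exploratory. Neither condition for bias is documented: no realised ratio and no drift in fat mass is reported. The illustration assumes a lasting step that begins exactly when allocation changes, whereas Table 4 shows a rise and fall, and language mix gives only about 1–11 g. Table 4 also stops at 298 women, while D3 expects about 600 at this site. Answering the primary aim separately in Spanish-speaking subjects, as D7d intends, would remove that one documented source, and D7c's adjusted model may absorb part of it. Period terms also cost precision: updates every 13 weeks over about 42 months give about 14 schedules.

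Most of this stands. It limits the point to D7c and to non-interaction DHA contrasts, and it argues against putting period terms into the primary interaction tests. It does not remove the point, because the plan relies on randomisation for those contrasts and randomisation holds only within a schedule.

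A reader might infer that Table 4 demonstrates drift in the outcome, or that adaptive allocation undermines the Aim 1 test. The documents support neither: Table 4 carries no fat-mass data, and the interaction is unbiased under common drift and nearly so otherwise.

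**Conclusion.** The gap is real, conditional and modest. D7c, and any high-versus-low DHA contrast overall or within excessive GWG, would pool allocation schedules that C1d allows to differ. Bias requires both a ratio that moved from 1:1 and fat mass that drifted over enrolment. Under a 0.3 SD step and 60–75% allocation it is 16–44 g for the overall contrast, with type I error 0.055–0.084 at n=240; at 0.1 SD it is negligible. The Aim 1 interaction test stands as planned, with type I error at most about 0.06 even when drift is confined to one GWG group.

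Two smaller points follow. D7d's equal-arms assumption is not guaranteed by C1d. The first-update triggers in C1d and C1e disagree, but this is secondary, because periods can be taken from the schedules actually used.

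**What to change.** - **Define period before arm and outcome are linked.** Use the allocation schedule in force when the mother was randomised. Merge adjacent schedules with similar ratios into about three or four periods, with the tolerance stated in advance. Across a 177 g step, merging two equal-sized schedules at 60% and 65% leaves 9 g of bias; merging 60% with 75% leaves 30 g.
- **D7c and any overall or within-GWG DHA contrast:** add period as a fixed factor.
- **D7a and D7b:** keep the interaction tests as planned. Pre-specify a sensitivity model with period and period × GWG, and in D7b also period × gender. An additive period term alone does not remove drift that differs between the groups being compared.
- **D7d:** state that 0.815 assumes about equal arms and that the realised ratio may differ.
- **C1d and C1e:** reconcile the first-update trigger.

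The cost is plan wording plus a schedule identifier for each woman. The appended tables in C1e should make this recoverable; that the parent trial would share it is an assumption. The precision cost falls on the sensitivity analysis and not on the primary test, and using few periods keeps it near 3%.
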